6.2. Spirometry

Subjects will have spirometry testing at the time of CARV infection and on months 1, 3, 6 and 12 (all $+/- 10$ days) following CARV infection. In addition, spirometry will be performed every 1-2 months ($+/- 10$ days) until month 12. Participants will also undergo spirometry testing when clinically indicated (new respiratory symptoms, pulmonary infiltrates, etc). Certified and trained technicians will conduct spirometry measurements according to American Thoracic Society (ATS) guidelines.

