Protocol:

A randomized placebo controlled trial of inhaled beclomethasone after community-acquired respiratory viral infection in lung transplant recipients

Version: 5

Date: 5.28.15

1. Abstract

The randomized placebo controlled trial of inhaled beclomethasone after community-acquired respiratory viral (CARV) infection in lung transplant recipients is a single center pilot study evaluating the impact of inhaled beclomethasone on the development and progression of chronic lung allograft dysfunction (CLAD) or death after CARV infection. The study will randomize 40 subjects to inhaled beclomethasone or placebo in a 1:1 ratio, and follow-up will be complete 12 months after randomization. The primary objective of the study is to determine if inhaled beclomethasone has greater efficacy than placebo for the endpoint of CLAD development or progression or death after randomization. The study will also assess multiple secondary endpoints including the safety and tolerability of inhaled beclomethasone in lung transplant recipients, respiratory viral symptom scores, the development of donor-specific human leukocyte antigen antibodies and antibodies to lung-specific self-antigens, and survival.

2. Background

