4.3. Study Objectives

Primary Objective

- To determine if inhaled beclomethasone has greater efficacy than placebo in preventing the composite endpoint of new or progressive CLAD or death 6 months after CARV infection in adult lung transplant recipients.

Secondary Objectives

- Incidence of new or progressive CLAD at 6 and 12 months after CARV infection
- Time to development or progression of CLAD
- Safety and tolerability of inhaled beclomethasone
- Respiratory viral symptoms
- Development of donor-specific HLA antibodies (DSA)
- Change in DSA mean fluorescence intensity
- Development of antibodies to lung-specific self-antigens (Collagen V and K- α 1 tubulin)
- Serum cytokine profiles
- Peripheral immune cell phenotypes
- Incidence of other bacterial, viral, or fungal infection at the time of CARV infection
- Incidence of acute rejection and lymphocytic bronchiolitis within 6 months following CARV infection
- Survival at 6 months (+ 10 days) and 12 months (+ 10 days) after CARV infection

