4.9. Endpoints

4.9.1. Composite Primary Endpoint

Freedom from new or progressive CLAD, or death 180 days after CARV infection.

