4.10. Outcomes Assessment

The development of CLAD is defined according to the following criteria:

- CLAD: FEV_1 and/or $FVC \leq 80\%$ baseline on 2 measurements obtained 3 weeks apart

Once CLAD has been established, it will be further defined by the following criteria:

- Restrictive CLAD (RAS): $FVC \leq 80\%$ baseline on 2 measurements obtained 3 weeks apart with an FEV_1/FVC ratio $\geq 75\%$
- Obstructive CLAD (BOS): $FEV_1 \leq 80\%$ baseline on 2 measurements obtained 3 weeks apart

Progressive CLAD is defined as a $\geq 15\%$ decrement in pre-CARV infection baseline FEV_1 or FVC . The pre-CARV infection baseline FEV_1 and FVC are defined as the average of the 2 most recent FEV_1 or FVC measurements separated by at least 3 weeks, and occurring within the 6 months prior to the diagnosis of the CARV infection. In the event that only 1 FEV_1 or FVC measurement is available in the previous 6 months, that value will serve as the pre-CARV infection baseline FEV_1 or FVC .

5. Treatments

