5.2.1. Active Study Drug

Inhaled beclomethasone (QVAR®, Teva Pharmaceuticals) 320mcg twice daily for 180 days. The first dose will be administered 7 ± 3 days after CARV infection.

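### The primary endpoint is counted from CARV infection, so a spirometry reading taken before randomization can be the first of the two that define new CLAD or, for progressive CLAD, a complete event

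*Combined protocol and SAP*

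**What the plan says.** - **Time origin.** Section 4.9.1 defines the primary endpoint as "Freedom from new or progressive CLAD, or death 180 days after CARV infection", and the primary objective in section 4.3 uses the same origin ("composite endpoint of new or progressive CLAD or death 6 months after CARV infection"). The abstract describes the same comparison as one "for the endpoint of CLAD development or progression or death after randomization".
- **Spirometry.** Section 6.2: "Subjects will have spirometry testing at the time of CARV infection and on months 1, 3, 6 and 12", each with a window of 10 days either side. There are further tests every 1 to 2 months and when clinically indicated.
- **Treatment start.** Section 5.2.1: "The first dose will be administered 7 ± 3 days after CARV infection". Section 5.2.2 gives placebo the same timing. Section 4.8 aims for randomization within 7 days of identifying the infection, and Table 1 allows 10 days.
- **Event rules.** Section 4.10 defines new CLAD as FEV1 and/or FVC at or below 80% "baseline on 2 measurements obtained 3 weeks apart". Progressive CLAD is a 15% or greater "decrement in pre-CARV infection baseline FEV_1 or FVC", with no second reading mentioned. The section does not say when the first qualifying reading may be taken or which reading dates the event.
- **Rejection.** A secondary objective in section 4.3 is "Incidence of acute rejection and lymphocytic bronchiolitis within 6 months following CARV infection". Section 8.3 allows CARV to be diagnosed on a bronchoscopy specimen.

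**The concern.** The trial asks whether treatment started after a CARV infection prevents new or progressive CLAD or death. Lung function measured before randomization describes the patient at entry and should not count as outcome. Section 5.4 anticipates acute loss: it plans for FEV1 falls of 10% or more at infection and lists such a fall among the signs of lower respiratory tract involvement. Eligibility does not remove patients who are already low at the CARV visit, because the BOS stage 3 exclusion in Table 1 is judged on the pre-CARV baseline.

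If entry readings can qualify, some primary events will have begun, and some may be complete, before treatment could act. Such events arise in both arms and shrink the difference between them. The abstract and sections 4.3 and 4.9.1 also permit two different event counts from the same data.

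**Working it through.** **Step 1. Timeline, with day 0 as CARV infection**

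| Item | Day | Source |
|---|---|---|
| Primary clock starts | 0 | 4.3, 4.9.1 |
| Infection-visit spirometry | about 0 | 6.2 |
| First dose | 7 − 3 = 4 to 7 + 3 = 10 | 5.2.1, 5.2.2 |
| Month-1 spirometry | 30 − 10 = 20 to 30 + 10 = 40 | 6.2 |
| Primary window ends | 180 | 4.9.1 |

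**Step 2. New CLAD.** I read the spacing as at least 21 days. A month-1 visit on day 21 to 40 can then confirm a low reading from day 0. A patient at 78% of baseline on day 0 and 79% at month 1 meets the rule, with the first reading taken before treatment. The confirming reading falls between 21 − 10 = 11 and 40 − 4 = 36 days after the first dose.

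**Step 3. Progressive CLAD.** One value at least 15% below the pre-CARV baseline satisfies the text. A day-0 reading can do this alone, 4 to 10 days before the first dose. The rule matters most for the BOS stage 1 and 2 stratum (section 4.8), whose size is not given.

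**Step 4. The plan's own figures.** Section 7 assumes 50% on placebo and an absolute reduction of 25%, so 50% against 25%. With 20 per arm that is 10 + 5 = 15 expected events. The pooled normal approximation at two-sided 5% (alpha is not stated, so assumed) is

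power = Φ{[|p1 − p2|√n − 1.96√(2p̄(1 − p̄))] / √[p1(1 − p1) + p2(1 − p2)]}.

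With n = 20 and p̄ = 0.375 this is Φ[(1.118 − 1.342)/0.661] = Φ(−0.34) = 37%, not the stated 80%. That shortfall is a separate matter. Here 37% serves only as the reference value.

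**Step 5. Dilution.** Let p be the share of each arm that becomes an event whatever the treatment. The documents give no value, so 10% and 20% are assumptions.

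- Reading A, events added on top of the planned rates: placebo p + (1 − p)(0.50), active p + (1 − p)(0.25).
- Reading B, the planned 50% already includes them and treatment halves the rest: placebo 0.50, active p + (0.50 − p)(0.50).

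| Reading | p | Placebo | Active | Difference (points) | Risk ratio | Power, 20 per arm |
|---|---|---|---|---|---|---|
| Planned | 0 | 50% | 25% | 25 | 0.50 | 37% |
| A | 10% | 55% | 32.5% | 22.5 | 0.59 | 30% |
| A | 20% | 60% | 40% | 20 | 0.67 | 24% |
| B | 10% | 50% | 30% | 20 | 0.60 | 25% |
| B | 20% | 50% | 35% | 15 | 0.70 | 16% |

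Section 7 states the 50% at 6 months after CARV infection, the same origin as the endpoint, which favors reading B.

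**The case against.** The strongest reply is that the new-CLAD rule already guards against a transient dip. A fall that has recovered by the second reading is not an event, and one that persists is confirmed on treatment. If the drug lifts the second reading above 80%, no event occurs. Section 2 proposes that viral injury starts the path to CLAD, so loss that persists after infection is arguably what the trial aims to prevent. This stands for new CLAD. It does not answer the progression rule, which has no confirmation.

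Several stronger readings are tempting, but the documents do not support them:

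- **Every viral dip counts as CLAD.** New CLAD needs a second low reading. Section 5.4 anticipates falls of 10% or more, which is short of either event threshold, and gives no frequency.
- **All such events are beyond the drug's reach.** That is certain only for an event completed before the first dose. For confirmed new CLAD it is an assumption, so the table overstates dilution to the extent that treatment can raise the second reading.
- **The result is biased toward one arm.** Allocation is 1:1, double blind and stratified by BOS stage. The expected effect is non-differential, although chance imbalance in acute FEV1 loss is possible with 20 per arm.
- **The Kaplan-Meier curves will show events before treatment, or a later recovery cannot cancel an event.** The first depends on a dating rule that is not given. On the second the text is silent, and a binary endpoint at 6 months could be read as status at that time.

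For rejection the case is weaker. Section 4.3 lists co-infection at the time of CARV infection but rejection as following it, so a biopsy at the diagnostic bronchoscopy may not be meant to count. A clarifying sentence is still needed.

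**Conclusion.** The point holds in this limited form. The time origin is inconsistent between the abstract and sections 4.3 and 4.9.1. As written, a reading from before randomization can supply the first half of a new-CLAD event or the whole of a progressive-CLAD event. This is more than missing detail, because it decides what counts as a primary event.

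The consequence is dilution of unknown size. Under assumed shares of 10% and 20%, the difference falls from 25 points to between 22.5 and 15, and power at 20 per arm falls from about 37% to between 30% and 16%. These figures rest on the assumed share, on treatment having no effect on those events, on two-sided 5%, and on which reading of the 50% is taken. With about 15 events expected, reclassifying a few could change the result.

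**What to change.** - Count primary events from randomization in sections 4.3 and 4.9.1, in line with the abstract. State whether the window closes 180 days after CARV infection or after randomization; under Table 1 the two differ by at most 10 days.
- State in section 4.10 that spirometry before randomization, including the CARV visit, cannot be a qualifying reading for new or progressive CLAD. The anchor should be randomization rather than first dose, since otherwise a patient randomized but never dosed could not have a CLAD event.
- Require progression to be confirmed by a second reading at least 3 weeks later, as for new CLAD.
- State which reading dates the event, and whether confirmation after the window closes counts.
- Count acute rejection and lymphocytic bronchiolitis only from biopsies after randomization.

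The visit schedule can stay as it is. I would not add a requirement that the low value persist to month 3: that rewrites the CLAD definition, and the gap closes without it.

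The cost is wording plus somewhat fewer or later counted events, so the placebo rate may fall below 50%. A loss that persists is still captured from month 1 onward and confirmed at a later scheduled test.

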6.3. Bronchoscopy

Bronchoscopy will only be performed if clinically indicated. Surveillance bronchoscopy to evaluate for occult acute rejection is performed at 1, 2, 3, 6, and 12 months after transplantation based on our clinical practice. In addition, bronchoscopy is performed to evaluate respiratory symptoms or clinical signs of allograft dysfunction (e.g.,

hypoxemia, pulmonary infiltrates, clinically significant decrements in spirometry). Bronchoscopy will not be performed for study reasons only.

6.4. HLA Antibody Testing

Participants will be tested for the development of donor-specific HLA antibodies (DSA) at enrollment, and at months 1, 3 and 6 (\pm 10 days for each time point) after CARV infection using the clinical assay in our center's histocompatibility laboratory. This will require a blood draw at those time points.

6.5. Testing for Antibodies to Self-antigens and Inflammatory Cytokines

At the same time points that testing is conducted for DSA (enrollment and months 1, 3 and 6 [\pm 10 days for each time point]), participants will be tested for the development of antibodies to collagen V and K- α 1 tubulin. In addition, participants' serum will be tested for a battery of pro-inflammatory and anti-inflammatory cytokines. This will be conducted in [name] research laboratory.

7. Statistical Considerations

We estimate an incidence of new or progressive CLAD of 50% at 6 months after CARV infection in the placebo group and an absolute risk reduction of 25% in the inhaled beclomethasone group. Therefore, a sample size of 40 subjects would provide 80% power. The primary endpoint of the development or progression of CLAD or death at 6 months will be evaluated as a binary endpoint and will be analyzed using the chi-squared method. In addition, the primary endpoint will be evaluated as a time to event analysis using the Kaplan-Meier method and the two groups will be compared using the log rank test. Secondary endpoints consisting of continuous data will be analyzed using either the Student's t-test or Mann-Whitney U Test and those consisting of categorical data will be analyzed using the chi-squared method.

8. Ethical Considerations and Safety

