Lung transplantation is the ultimate treatment for patients with advanced lung disease. However, long-term outcomes remain disappointing, and the median survival after transplantation is approximately 5.5 years. While infection and graft failure are the leading causes of death in the first year after transplantation, chronic rejection is the leading cause of death beyond the first year. Chronic rejection after lung transplantation is characterized histologically as obliterative bronchiolitis, although histologic confirmation is difficult. Therefore, chronic lung allograft syndrome (CLAD) and bronchiolitis obliterans syndrome (BOS), defined and staged based on changes in spirometry measurements, are the clinical surrogates of chronic rejection after lung transplantation. The incidence of CLAD approaches 50% at 3 years after transplantation, and there is no effective evidence-based treatment. Unfortunately, this results in a progressive and relentless decline in lung function culminating in graft failure and death. Indeed, the median survival after the diagnosis of CLAD is 3 years, and studies have consistently demonstrated a significantly reduced quality of life in patients with CLAD. Clearly, CLAD is the leading obstacle to better outcomes after lung transplantation, and lung allograft recipients urgently need strategies to prevent or delay the onset of CLAD.

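### Section 7 takes its sample size inputs from CLAD alone, but the primary test is on CLAD or death, so the stated 80% power does not describe the primary analysis

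*Combined protocol and SAP*

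**What the plan says.** The sample size paragraph in Section 7 starts from CLAD: "We estimate an incidence of new or progressive CLAD of 50% at 6 months after CARV infection in the placebo group". It then supposes that beclomethasone lowers this rate by 25 percentage points, and concludes that "a sample size of 40 subjects would provide 80% power". The Abstract shows that 40 is the total: "The study will randomize 40 subjects to inhaled beclomethasone or placebo in a 1:1 ratio", so 20 per arm.

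The next sentence of Section 7 describes a different event: "The primary endpoint of the development or progression of CLAD or death at 6 months will be evaluated as a binary endpoint", to be compared by chi-squared. Section 4.9.1 agrees, defining the primary endpoint as "Freedom from new or progressive CLAD, or death 180 days after CARV infection". The hypotheses in Section 4.2 and the primary objective in Section 4.3 also include death.

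CLAD without death appears separately among the secondary objectives in Section 4.3, as "Incidence of new or progressive CLAD at 6 and 12 months after CARV infection", and again among the secondary endpoints in Section 4.9.2.

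No section gives a 6-month death rate, a rate of death without CLAD, or a composite rate for either arm. Nothing says that the 50% and 25% already include deaths. Alpha is not stated. The alternative hypothesis in Section 4.2 is two-sided.

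**The concern.** The protocol treats CLAD alone and CLAD or death as two endpoints, takes its sample size inputs from the secondary one, and tests the primary one. A patient who dies without new or progressive CLAD counts in the primary analysis but not in the rates used for planning. The composite rates in the two arms, and the difference between them, are therefore undefined in the plan.

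Two things are at stake. First, the power figure gives the reader a benchmark for a null primary result, and this benchmark belongs to another endpoint. Second, recalculating the power from 50% and 25% would not cure this, because the new figure would still describe CLAD alone. The input rates have to be settled before the power is recomputed.

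**Working it through.** **Inputs.** CLAD at 6 months is 50% on placebo and 50% − 25% = 25% on beclomethasone (Section 7), with 20 per arm (Abstract). I assume a two-sided alpha of 5%: the sidedness follows Section 4.2, and the level is not stated.

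**Step 1: the plan's own figure.** With n per arm and mean rate p̄ = 0.375, the pooled normal approximation is

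power = Φ{[δ√n − 1.96√(2p̄(1−p̄))] / √(p₁(1−p₁) + p₂(1−p₂))}

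- Numerator: 0.25 × √20 − 1.96 × √0.46875 = 1.118 − 1.342 = −0.224.
- Denominator: √(0.25 + 0.1875) = 0.661.
- Power: Φ(−0.339) = 36.8%.

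Exact binomial enumeration of the uncorrected chi-squared test gives 37.5%. The stated 80% is not reproduced. By the same approximation, 80% power for 50% vs 25% needs (1.342 + 0.842 × 0.661)² / 0.0625 = 57.7, so 58 per arm. Reading 40 as a per-arm number gives 64%. With 20 per arm and 50% on placebo, 80% power requires about 10% on treatment, a 40-point difference.

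**Step 2: from CLAD to the composite.** Let d_P and d_B be the 6-month risks of death among patients without new or progressive CLAD, on placebo and beclomethasone.

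- Placebo composite rate = 0.50 + 0.50 d_P
- Beclomethasone composite rate = 0.25 + 0.75 d_B
- Difference = 0.25 + 0.50 d_P − 0.75 d_B

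The difference is below 25 points when d_B exceeds two thirds of d_P, equals 25 points at exactly two thirds, and is above 25 points below that.

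**Step 3: a range for d.** The documents give no CLAD-free death risk, so I use 1%, 3% and a proxy. Section 2 says that "the median survival after transplantation is approximately 5.5 years". Under a constant hazard, the 6-month risk is 1 − 0.5^(0.5/5.5) = 6.1%. This counts all deaths, including those after CLAD, so I use it as the upper end of the range.

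**Step 4: power on the composite, 20 per arm (exact, uncorrected chi-squared, two-sided 5%).**

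| CLAD-free death risk, placebo | Drug effect on that risk | Composite rates | Difference (points) | Power |
|---|---|---|---|---|
| 0% | – | 50.0% vs 25.0% | 25.0 | 37.5% |
| 1% | none | 50.5% vs 25.75% | 24.75 | 36.5% |
| 3% | none | 51.5% vs 27.25% | 24.25 | 34.4% |
| 6.1% | none | 53.1% vs 29.6% | 23.5 | 31.5% |
| 6.1% | lowered by one third | 53.1% vs 28.1% | 25.0 | 35.6% |
| 6.1% | halved | 53.1% vs 27.3% | 25.8 | 37.8% |

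With no drug effect on CLAD-free death, the further loss is 1 to 6 percentage points of power. If the risk is lowered by a third, the difference holds, and power is about 2 points lower only because both rates move toward 50% and the variance rises. If it is halved, there is no loss.

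**The case against.** The strongest reply is that the consequence depends on an assumption the plan does not make. A reader might infer that CLAD-free deaths must dilute the 25-point difference, or that the plan assumes no drug effect on them. Neither inference is supported. Section 7 is silent on deaths in the sizing, and Sections 4.1 and 4.3 set out to prevent the composite, death included. As Step 2 shows, the difference can shrink, hold or widen, and the documents give no figure to choose between these. This stands: the dilution is conditional.

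The size of the proxy is also open to challenge. The 6.1% is all-cause mortality counted from transplantation. Section 2 names chronic rejection as the leading cause of death after the first year, so many of those deaths would follow CLAD and may already be composite events. It might be tempting to go higher by using the median survival after a CLAD diagnosis, also in Section 2. That is mortality after CLAD, not death without it, and does not belong in this calculation.

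The mismatch is, moreover, the smaller of two faults. Power is about 37% for the stated rates before any death is counted, so aligning the endpoint would not restore 80%.

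Finally, the omission of death may be loose wording, with 50% and 25% meant as composite rates. That is possible, though nothing in the documents says so. Two added words would then settle the mismatch, but the 80% would still not follow from those rates.

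None of this removes the central point. The planning rates are worded for one endpoint, the primary test is on another, and no rate is given for the one tested.

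**Conclusion.** The mismatch is established from the text. Section 7 takes its inputs from CLAD alone, a secondary endpoint, and tests CLAD or death, so the 80% does not describe the primary analysis. Nor does it describe CLAD alone: 20 per arm gives about 37% for 50% vs 25%, at an assumed two-sided 5%.

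The extra effect of CLAD-free deaths is modest and conditional. If their risk is the same in both arms, power falls to about 36% at 1%, 34% at 3% and 32% at 6%. If the drug lowers that risk by about a third, the difference stays near 25 points; with a larger effect it widens. These figures rest on my assumptions about CLAD-free death and on a proxy mortality figure, not on anything the plan states. The conclusion is that the plan must say which composite rates it assumes, not that those rates must differ by less than 25 points.

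**What to change.** In Section 7:

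- State the assumed 6-month rate of CLAD or death in each arm, with the assumption about CLAD-free deaths behind it, including whether the drug is expected to change them. As an illustration, CLAD at 50% vs 25% with a 6% CLAD-free death risk common to both arms gives 53% vs 29.5%.
- Alternatively, if 50% and 25% were meant as composite rates, add *or death* to the sentence and accept that the implied rates for CLAD alone are no higher, and are lower wherever some deaths occur without CLAD.
- State alpha and sidedness.
- Replace the 80% with the recomputed power for the composite with 20 per arm, or with the difference that 20 per arm can detect.

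The cost is a few sentences and one recalculation. Enrolment, treatment and the planned tests stay as they are. The downside is a less favourable stated power.

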4.2. Hypotheses

Null Hypothesis There is no difference in incidence of new or progressive CLAD, or death between the two randomized treatment groups (placebo = inhaled beclomethasone)

Alternative There is a statistically significant difference in the incidence of new or progressive CLAD, or death between the two randomized treatment groups (placebo ≠ inhaled beclomethasone)

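### Section 7 claims 80% power from 40 subjects, but its own assumptions give about 37% at a two-sided 5% level

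*Combined protocol and SAP*

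**What the plan says.** The sample size rationale is in section 7 (Statistical Considerations). It starts from a placebo rate: "We estimate an incidence of new or progressive CLAD of 50% at 6 months after CARV infection in the placebo group". It adds the effect to be detected, "an absolute risk reduction of 25% in the inhaled beclomethasone group", and concludes: "Therefore, a sample size of 40 subjects would provide 80% power". The same section says that the primary endpoint, CLAD development or progression or death at 6 months, "will be evaluated as a binary endpoint and will be analyzed using the chi-squared method". A Kaplan-Meier analysis is added, in which "the two groups will be compared using the log rank test".

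The abstract (section 1) fixes what the 40 means: "The study will randomize 40 subjects to inhaled beclomethasone or placebo in a 1:1 ratio". Section 4.5 repeats 40 as the number to be enrolled. Section 4.2 states the null as "placebo = inhaled beclomethasone" and the alternative as any difference between the arms, so the test is two-sided. Neither a significance level nor a dropout allowance is given anywhere.

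**The concern.** Twenty subjects per arm is very few for a comparison of 50% with 25%, where the expected counts are 10 events against 5. The word 'therefore' in section 7 presents the 80% as following from the stated rates, so it can be checked directly, and it does not follow.

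This is the only justification given for the sample size, and it concerns the primary endpoint. Someone who relies on 80% power may treat a non-significant result as reasonable evidence that the assumed benefit is absent. If the true power is below 40%, such a result says little. The ethics board approving the protocol would also be working from a wrong account of what the trial can show.

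**Working it through.** **Inputs**

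- n = 20 per arm: 40 in total, 1:1 (sections 1 and 4.5).
- p1 = 0.50 on placebo; p2 = 0.50 − 0.25 = 0.25 on beclomethasone (section 7).
- Chi-squared test on a binary endpoint (section 7), two-sided alternative (section 4.2).
- Alpha: not stated. I assume 0.05 two-sided (z = 1.960) and vary it below.

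**Attempt to reproduce the 80%**

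The usual pooled-variance formula is

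power = Φ{ [d√n − z·√(2p̄(1−p̄))] / √(p1(1−p1) + p2(1−p2)) }

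with d = 0.25 and p̄ = 0.375.

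- Null SD term: √(2 × 0.375 × 0.625) = 0.6847.
- Alternative SD term: √(0.25 + 0.1875) = 0.6614.
- d√n = 0.25 × 4.472 = 1.1180.
- Power = Φ[(1.1180 − 1.960 × 0.6847)/0.6614] = Φ(−0.338) = **36.8%**.

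Full enumeration of the 21 × 21 possible tables at two-sided 0.05 gives 37.5% for the uncorrected chi-squared test, 23.9% with continuity correction and 26.9% for Fisher's exact test. Section 7 does not say whether a correction applies.

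**Other readings of the plan** (pooled formula)

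| Reading | Power |
|---|---|
| 20 per arm, one-sided 0.05 (= two-sided 0.10) | 49.5% |
| 20 per arm, two-sided 0.20 (= one-sided 0.10) | 64.2% |
| 20 per arm, one-sided 0.20 | 79.4% |
| 40 per arm, two-sided 0.05 | 64.1% |
| 40 per arm, one-sided 0.05 | 75.4% |
| 40 per arm, two-sided 0.20 (= one-sided 0.10) | 85.6% |

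With 20 per arm, 80% requires z = (1.1180 − 0.8416 × 0.6614)/0.6847 = 0.820. That is a two-sided alpha of about 0.41, or about 0.21 one-sided.

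**Log-rank test.** With 20 × 0.50 + 20 × 0.25 = 15 expected events and, assuming proportional hazards, HR = ln 0.75 / ln 0.50 = 0.415, Schoenfeld's formula gives Φ(√(15/4) × |ln 0.415| − 1.960) = Φ(1.703 − 1.960) = 39.9%. The additional analysis is no better powered.

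**Adding death to the planning rate.** The 50% is given for CLAD alone, while the endpoint includes death. Raising both arms by 5 points (55% vs 30%) gives 35.5%; by 10 points (60% vs 35%), 34.9%. The shortfall remains.

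**What 80% would take at two-sided 0.05**

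- n per arm = [(1.960 × 0.6847 + 0.8416 × 0.6614)/0.25]² = 57.7, so 58 per arm, 116 in total. With continuity correction it is 65.4, so 66 per arm, 132 in total. Neither allows for dropout.
- With 20 per arm and 50% on placebo, the pooled formula reaches 80% at p2 = 0.105, a reduction of 39.5 points.

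**Precision.** If exactly 25 points were observed, SE = √(0.4375/20) = 0.148, and the 95% interval is 0.25 ± 1.96 × 0.148, about −4 to +54 points.

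**The case against.** The strongest reply has three parts.

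First, alpha is not in the documents, so 37% depends on an input I supplied. That is true and must be stated. But power stays below 50% at one-sided 0.05. The only setting tried with 40 in total that comes close to 80% is one-sided 0.20, which is stated nowhere and conflicts with the two-sided alternative in section 4.2. Reading 40 as a per-arm number contradicts section 1, and still falls short at 0.05.

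Second, the study is labelled a pilot (sections 1 and 4.1), and a pilot may be small. That excuses the sample size but not the statement about it. Sections 4.1 to 4.3 set a formal efficacy aim and hypothesis, and section 7 defends the size by power.

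Third, no text says that a null result will be read as no benefit. That is fair: the misreading is a risk I infer from how power statements are normally used. It is also fair that making the risk difference the primary result would change the planned analysis, which correcting this error does not require. The mismatch between the CLAD-only rate and the composite endpoint is real but does not explain the shortfall.

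**Conclusion.** The 80% figure is wrong. On the plan's own rates, allocation and test, power is about 37%, a shortfall of some 43 percentage points, and a true 25-point benefit would be missed in about 63% of such trials. This rests on an assumed two-sided alpha of 0.05, the uncorrected chi-squared test and no dropout. A continuity correction or Fisher's test lowers power to 24–27%, and losses to follow-up would lower it further. The conclusion does not depend on the exact alpha: no conventional level, one- or two-sided, gives 80% with 40 subjects in total. This must be corrected, because it is the stated basis for the size of the trial.

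**What to change.** Replace the power sentence in section 7 with wording such as: *With 20 subjects per arm and a two-sided alpha of 0.05, the uncorrected chi-squared test has about 37% power to detect 50% versus 25%; with a 50% placebo rate, 80% power is reached only if the beclomethasone rate is about 10.5% or lower.* If a continuity correction or Fisher's test is intended, name it and use its figures (24% or 27%). The detectable difference must then be recalculated as well: at 50% versus 10%, exact power is 84% uncorrected, but 73% with correction and 74% with Fisher's test.

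Add that the trial is a pilot not powered for a 25-point difference, and that a non-significant p-value will not be taken as evidence of no effect. State the assumed placebo rate for the composite including death.

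Reporting the risk difference with its 95% confidence interval beside the chi-squared test is advisable, and can be done without changing the primary analysis.

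The cost is a protocol wording amendment and a less favourable power statement. Enrolment, treatment and follow-up do not change.
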